**Secondary Outcome 1: Proportion of cases receiving a packed red blood cell transfusion throughout the study period.**

An analysis similar to that for Primary Outcome 1 will be used to determine if there was a difference in trend over time for the proportion of cases receiving a pRBC transfusion. A similar analysis will be conducted at the institution level.

The proportion of people transfused at each hemoglobin threshold level (<6, 6-7, 7-8, 8-9, 9-10, >10) will be compared between 2012 and 2016 to determine if a change in practice occurred using a Chi-square or Fisher's Exact test, as appropriate.

**Secondary Outcome 2: The number of units of packed red blood cells transfused during the intraoperative period.**

The number of units of pRBC transfused during the intraoperative period will be analyzed similar to Primary Outcome 1.

To determine independent predictors of the number of units of pRBC transfused during a case, two mixed effects linear regression models will be constructed with the independent covariates listed in the methods and the dependent variable of number of units of packed red blood cells transfused. The first model will contain the mixed effect of institution, and the second model will contain the hierarchical mixed effects of primary attending nested within institution.

**Secondary Outcome 3: The nadir postoperative hemoglobin (lowest value measured 0 – 72 hrs after the completion of intraoperative anesthesia care)**

The lowest postop hemoglobin will be examined for a trend over time for all cases using a Joinpoint analysis as for previous outcomes. The lowest postop hemoglobin will be compared at each time point between those with and without an intraoperative transfusion using a Student's t test or Mann-Whitney U test, as appropriate.

**Secondary Outcome 4: The relationship between patient, surgical and institutional factors and the occurrence of transfusion and determination of the subsequent impact of any transfusion trends on blood product utilization.**

Two mixed-effects logistic regression models will be used to determine if surgery type, year, and cardiac disease are independent predictors of intraoperative transfusion. The outcome of intraoperative transfusion will be defined as any PRBC use between Anesthesia Start and

Anesthesia End. The first model will contain the mixed effect of institution, and the second model will contain the hierarchical mixed effects of primary attending nested within institution. Independent variables to be included in the model are: Age, Sex, Elixhauser co-morbidities (as numeric and also CAD y/n, heart failure y/n, cancer y/n), WHO BMI classifications, ASA Status, Pre-op Hb, lowest Intra-op Hb for cases without intraop transfusion or the pre-transfusion hemoglobin, Pre-op Plts (abnormal y/n), Pre-op Creatinine (abnormal y/n), Abnormal coags (y/n – PT, PTT or INR), Surgical Specialty, EBL, Cell saver (Scavenged) blood use (y/n), Emergent Surgery, Use of anti-fibrinolytics (Aminocaproic Acid, Tranexamic Acid, Aprotinin) – y/n, and surgical Case Duration.

To determine if transfusion practice changed over time, a multivariable linear regression model will be constructed as above, with the outcome of intraoperative hemoglobin (lowest throughout the case for those who were not transfused and prior to transfusion as defined above for those who received an intraop transfusion). The covariate of intraoperative transfusion y/n will be added to the list specified above. Model-based least square means with standard error will be reported and compared between those who were transfused and those who were not with a Student's t test. These means are the adjusted marginal mean of the outcome for the population, which we will consider a proxy for transfusion threshold. A one-way t-test will be used to test if the model-based mean hemoglobin for those who were transfused changed over time.

An observed vs. expected analysis will be conducted for the occurrence of transfusion, comparing practice patterns between the first and last time periods (quarters/half-years/years as appropriate) using a Chi-squared or Fisher's Exact test.

**Secondary Outcome 5: The relationship between in hospital mortality, post-operative myocardial injury, acute kidney injury and intraoperative hemoglobin concentration (with and without transfusion).**

Due to the small sample size expected for in-hospital mortality and post-operative myocardial infarction, the outcome for this analysis will be a composite variable of post-operative morbidity and mortality. Multiple mixed-effects logistic regression models will be used to determine if perioperative hemoglobin is an independent predictor of post-operative morbidity and mortality in ranges which are typically considered consistent with restrictive transfusion. In one model the lowest intraoperative hemoglobin will be considered as a continuous variable, for modelling outcome, in another, we will compare lowest intraoperative hemoglobin ranges of <6 g/dL, 6-7 g/dL, 7-8 g/dL, 8-9 g/dL, 9-10 g/dL, > 10 g/dL. Due to sample size constraints, we may have to redefine these boundaries. We will further analyze this to include the mixed effect of institution, and the second model will contain the hierarchical mixed effects of primary attending nested within institution. All models will include transfusion as a binary variable.

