We hypothesized that: 1) We would observe a reduction in pre-transfusion intraoperative hemoglobin, as a proxy for transfusion trigger, and reduction in nadir hemoglobin in cases where intraoperative transfusion was not performed. 2) A diminishing number of intraoperative transfusions would be observed, overall and at each hemoglobin value. 3) There would be a reduction in the nadir postoperative hemoglobin. 4) That any observed trends would be modulated by year, surgery type, institution and the presence of coronary artery disease. 5) That in the presence of a change in transfusion practice, we would not observe a change in mortality, post-operative myocardial injury or acute kidney injury.

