## Methods:

The MPOG Consortium assembles a database of perioperative information of patients undergoing anesthetic care at institutions across the US and the Netherlands. Data is assembled from electronic health record systems (including anesthesia specific systems), administrative, laboratory and outcome data sources. Full details of the functioning of the MPOG Consortium are described elsewhere. IRB approval for this study is provided by University of Michigan Institutional Review Board (HUM00052066). Sites participating in the MPOG collaborative obtain local IRB approval to assemble, organize and transmit this dataset. In keeping with the normal operating procedure of the MPOG collaborative the study protocol was presented to and approved by the MPOG Perioperative Clinical Research Committee (PCRC) on October 9th 2017. It was finalized on Feb 2nd 2018, prior to data extraction or analysis. A completed STROBE checklist for this study is attached to this manuscript (Appendix 1).

Sites will be included if they participated in the MPOG collaborative and data, including perioperative labs, and hospital and professional billing data were consistently available for the period between January 1, 2012 and July 1, 2017. We anticipate including data from 8 participating US sites: Cleveland Clinic, University of Colorado, University of Michigan, University of Oklahoma, University of Tennessee, University of Vermont, University of Virginia and Vanderbilt University.

Subjects will be included in the study if they were 18 years or older at time of surgery, underwent an orthopedic, general, transplant, vascular, gynecologic, urologic, neurosurgery, plastic, ENT or thoracic procedure with an associated inpatient stay. Subjects will be excluded if they underwent transfusion of greater than 3 units of packed red blood cells during the intraoperative period, underwent outpatient surgery, cardiac surgery, obstetric surgery, any procedure involving CPB or were assessed as having an ASA physical status classification of 5 or 6. Case groupings will be performed based on Anesthesia CPT Codes (see Appendix 2).

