The primary outcomes of this study are: the change in the pre-transfusion hemoglobin (ie transfusion threshold) and the nadir hemoglobin not-followed with an intraoperative transfusion over the course of the study period. The secondary outcomes of this study are: proportions of cases receiving a packed red blood cell transfusion throughout the study period (including stratification by prior laboratory measurements); the number of units of packed red blood cells transfused during the intraoperative period; the nadir postoperative hemoglobin (lowest value measured 0 – 72 hrs after the completion of intraoperative anesthesia care), the relationship between patient, surgical and institutional factors and the occurrence of transfusion and determination of the subsequent impact of any transfusion trends on blood product utilization; the relationship between in hospital mortality, post-operative myocardial injury, acute kidney injury and the pre-transfusion hemoglobin (for transfused cases – definition below) and lowest (for non-transfused cases) intraoperative hemoglobin.

In this study, we define coronary artery disease based on the present of a discharge ICD9/10 as listed in Appendix 3. Determination of AKI was based on the KIDIGO laboratory based definition AKI (Cr rise of 0.3 mg/dL rise within 48hrs of anesthesia end time or rise by more than 50% in 7 days). We will use intraoperative hemoglobin values documented, regardless of method of measurement. We preferentially use hemoglobin measures over hematocrit if these are documented simultaneously. If only a hematocrit is present at the time of lab measurement, we will perform an estimated conversion to hemoglobin, by dividing by 3. For blood transfusions documented exclusively in volume based units, we will convert this to units by assuming that any blood volume transfused greater than or equal to 250ml and less than or equal to 450 ml in one charting increment corresponds to one unit of blood.

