### **Primary Outcome 1: The change in documented hemoglobin prior to an intraoperative transfusion.**

The hemoglobin of interest for this outcome is the pre-transfusion hemoglobin. See additional definitions above. Additionally, for this primary outcome we will perform a sensitivity analysis, following the same statistical methodology, to compare the effect of including only the first transfusion of the case in those cases with multiple transfusion with our definition.

First, the trend of median pre-transfusion hemoglobin measurement by quarter will be assessed for any change over time by testing whether the slope is significantly different from 0 using a bivariate linear regression model with the dependent variable of median pre-transfusion hemoglobin measurement. If the slope is not significantly different from 0, then the analyses for this aim will conclude. Otherwise, a Joinpoint analysis will be conducted to determine if there are any inflection points in the trend. If no inflection points are found and the slope is negative and significantly different from 0, then Hypothesis 1 will be assumed true. If the Joinpoint analysis finds one or more inflection points in the data, then a Student's t test or Mann-Whitney U test will be used to compare the values between consecutive quarters to analyze the significance of the change. A similar analysis will be conducted at the institution level.

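### The unadjusted units trend in Secondary Outcome 2, read as a quarterly median of a 0–3 count, is nearly uninformative, and the >3-unit exclusion biases the blood-use trends

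*Protocol*

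**What the plan says.** The Introduction's second hypothesis is that "A diminishing number of intraoperative transfusions would be observed, overall and at each hemoglobin value". Two secondary outcomes carry it most directly.

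- **Secondary Outcome 2 (units), trend:** "The number of units of pRBC transfused during the intraoperative period will be analyzed similar to Primary Outcome 1". No other summary statistic is named, nor whether the denominator is all cases or transfused cases.
- **The method referred to (Primary Outcome 1):** "First, the trend of median pre-transfusion hemoglobin measurement by quarter will be assessed for any change over time", by linear regression on quarter. Then: "If the slope is not significantly different from 0, then the analyses for this aim will conclude".
- **Secondary Outcome 1 (proportion transfused):** "An analysis similar to that for Primary Outcome 1 will be used".
- **Eligibility (Methods):** "Subjects will be excluded if they underwent transfusion of greater than 3 units of packed red blood cells during the intraoperative period". Volume-only records are turned into whole units: 250 to 450 ml "in one charting increment corresponds to one unit of blood".
- **Models of units (Secondary Outcome 2):** two case-level mixed-effects linear models are also planned to find independent predictors. Statistical Analysis puts calendar time into all models as a fixed effect. Both covariate lists (Methods and Statistical Analysis) also include hemoglobin, which Methods specifies as the nadir.

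The protocol describes no analysis that keeps the cases above 3 units.

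**The concern.** A median suits hemoglobin, which is close to continuous. It suits poorly a count with four possible values, most of them probably zero, because it can stay fixed while the mean moves appreciably. The stop rule then ends the trend analysis on a flat slope that says little about blood use.

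The exclusion is a second and separate problem. Units transfused is both the outcome and an eligibility criterion. If practice moves toward fewer units per case, some cases that would have been excluded at 4 units are included at 3. The cohort then gains heavily transfused cases because use has fallen.

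At stake are the second hypothesis and the statement on blood-product utilization under Secondary Outcome 4. A flat or rising result could be read as no change in blood use when use had in fact declined.

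**Working it through.** **Inputs from the protocol.** January 2012 to July 2017 is 22 quarters. About 113,000 cases gives 113,000/22 ≈ 5,136 per quarter. Units run 0–3 after exclusion. Sample Size gives no alpha, transfusion rate, unit distribution or effect size, so there is no power figure to reproduce. All rates and unit distributions below are assumptions.

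**1. Median over all cases.** If the share transfused is below 50%, more than half the values are 0 and the median is 0, whatever the unit distribution. In simulation (22 × 5,136 cases, 200 runs per scenario, two-sided 0.05 assumed) it was constant in 100% of runs, even with the true rate halving from 40% to 20%. The slope is then exactly 0.

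**2. Median among transfused cases.** Let s be the single-unit share, with the rest split 3:1 between two and three units (assumed). Mean units = s + (1 − s) × (0.75 × 2 + 0.25 × 3) = s + 2.25(1 − s).

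- s from 36% to 48%: mean 1.80 to 1.65 (−8%); median 2 throughout.
- s from 52% to 68%: mean 1.60 to 1.40 (−12.5%); median 1 throughout.

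In simulation, a fall in mean units from 1.53 to 1.42 left the median constant in 100% of runs, while the quarterly mean was significant in 100%. If s crosses 50%, the median drops from 2 to 1. That was significant in 100% of runs at a fixed 20% rate, and in 96.5% when the rate also fell to 12%.

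The protocol's Introduction reports a European study in which 41% received more than one unit, so about 59% received one. If US practice were similar, the median would start at 1 and could not fall further.

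**3. The exclusion.** Let p be the true share transfused, f(k) the share of transfused cases receiving k units, and q the share receiving more than 3. In the restricted cohort:

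- share transfused = p(1 − q)/(1 − pq)
- mean units per case = p × [f(1) + 2f(2) + 3f(3)]/(1 − pq)

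With p fixed, the first expression rises as q falls: its derivative in q is −p(1 − p)/(1 − pq)², which is negative. The direction is therefore structural; only the size depends on assumptions.

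*Worked example.* Per 1,000 cases, assume 900/35/35/12 with 0/1/2/3 units and 9/5/4 with 4/5/6.

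- All cases: 35 + 70 + 36 + 36 + 25 + 24 = 226 units, or 22.6 per 100 cases.
- Restricted: 141/982 = 14.36 per 100; share transfused 82/982 = 8.35%. Excluded cases hold 85/226 = 38% of units.
- 30% of multi-unit cases receive one unit fewer: true use is (226 − 0.3 × 65)/1,000 = 20.65 per 100 (−8.6%). Restricted use is 135.0/984.7 = 13.71 (−4.5%); share 84.7/984.7 = 8.60%, although nobody changed transfusion status.
- Only >3-unit cases reduced, again 30% by one unit: true use is (226 − 5.4)/1,000 = 22.06 (−2.4%). Restricted use is 149.1/984.7 = 15.14 (+5.5%).

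*Other assumed distributions, from the formulas above:*

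| Scenario | True units per case | Restricted units per case | Restricted share transfused |
|---|---|---|---|
| p 20% fixed; q 20% to 15%, units falling | 0.480 to 0.424 (−12%) | 0.285 to 0.278 (−2.5%) | 16.7% to 17.5% |
| p 20% fixed; 4-unit cases move to 3, q 20% to 10% | 0.440 to 0.420 (−4.5%) | 0.292 to 0.347 (+19%) | 16.7% to 18.4% |
| p 20% to 12%; q 20% fixed | 0.480 to 0.288 (−40%) | 0.285 to 0.168 (−41%) | 16.7% to 9.8% |
| p 20% to 12%; q 20% to 15% | 0.480 to 0.254 (−47%) | 0.285 to 0.165 (−42%) | 16.7% to 10.4% |

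In row 1 the restricted mean was significant in 15% of runs and the spurious rise in the share in 54%. In rows 3 and 4 the fall in the share was significant in 100%. Replacing the median by a mean therefore does not cure the exclusion.

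**The case against.** A reader might infer that the blood-use outcomes cannot show a change whatever happens. The documents do not support that. Secondary Outcome 1 is a proportion and registers a real fall in rate. The mixed linear models of units have a time term. A median among transfused cases can jump from 2 to 1. Hypothesis 2 is also addressed by the 2012 versus 2016 comparison within hemoglobin strata, the logistic models and the observed-versus-expected analysis.

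The median is also an inference. Primary Outcome 2 is to be analyzed identically to Primary Outcome 1, whereas Secondary Outcomes 1 and 2 are only to be analyzed similarly. For a proportion, that cannot mean a median. A statistical analysis plan might name another summary. This has force, but the only method the protocol points to for units is the median one, so the text needs correcting where it stands.

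Nor does the stop rule cancel the mixed models. They are a separate paragraph with a separate purpose, and nothing makes them conditional on the slope. However, their time coefficient is the change in units at a given hemoglobin. Transfusing at a lower hemoglobin, the mechanism of Hypothesis 1, is partly adjusted away. They also use the truncated cohort.

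Finally, the 3-unit limit is a declared eligibility rule, and every magnitude above is assumed. It would be too strong to say that it always biases against a reduction: with q constant, a 40% fall in rate appears as 41%. The bias arises when the share above 3 units falls.

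**Conclusion.** The point holds in two parts, both confined to secondary outcomes.

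1. Read as written, the unadjusted units trend is nearly uninformative. Over all cases it is fixed at 0 if fewer than 50% are transfused, which needs no assumption about units. Among transfused cases it is a step function that missed falls in mean units of 8% and 12.5% in the assumed examples.
2. The >3-unit exclusion selects on the outcome. When units per case fall, it can attenuate the units trend (−8.6% seen as −4.5%; −12% as −2.5%) or reverse it (−2.4% seen as +5.5%). It also slightly inflates the proportion transfused (8.35% to 8.60%, or 16.7% to 17.5%, with the true rate flat). Secondary Outcome 1 is thus biased but not blind.

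The direction of the effect on the proportion follows from algebra. All sizes rest on assumed distributions, since the protocol gives none. The primary hemoglobin outcomes are not affected by this point.

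**What to change.** - **Units trend.** In Secondary Outcome 2, replace the reference to the Primary Outcome 1 method by a trend in quarterly mean units per case and per transfused case, with each denominator named. A case-level count model or ordinal model with time would also serve. Replacing the planned mixed linear models is optional.
- **Exclusion.** Repeat Secondary Outcomes 1 and 2 and the blood-utilization statement with >3-unit cases retained, using a cap or a top category, and report the share of cases above 3 units by quarter. Keep the exclusion for the hemoglobin-threshold outcomes.

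The cost is small: the extract must keep the >3-unit cases, one trend analysis changes and a few are repeated. A few massive-bleed cases will add variance, which the cap or top category limits.

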For those transfused, the hemoglobin analyzed will be the value immediately prior to the transfusion of the case. In the cases with multiple transfusions, it will be the highest of the identified pre-transfusion hemoglobin measures across each of the transfusions. We will define immediately prior to transfusion as the lab value drawn closest to transfusion within a 30-minute pre-transfusion window. If this proves too restrictive and more than 30% of pre-transfusion lab values will be excluded, the window will be liberalized to 45 minutes. The hemoglobin measurement identified is referred to as the “pre-transfusion hemoglobin” throughout this document. For those who were not transfused, the nadir hemoglobin will be the lowest value of the case.

The covariates to be included in all models (discussed below) are surgical specialty (defined based on anesthesia CPT Code assigned to the case), age, BMI, sex, presence of coronary artery disease (defined by ICD 9/10 codes), Elixhauser comorbidities, quarter of the study period, and nadir hemoglobin. The unit of measure for time used in trend analysis will be by quarter. The use of autologous blood will not be considered in this analysis. Patients who receive exclusively cell saver blood (and no PRBCs) will be considered not to be transfused for the purposes of the analysis.

We will describe the proportion of cases with a non-red blood cell blood product administered and the frequency of use of measures of coagulation (PT/INR, PTT, PLTs etc) as documented in the anesthesia record and the use of “cell saver” blood. Additionally, we will perform a survey of participating institutions to determine if formal blood transfusion protocols or blood transfusion management efforts, pre-operative preparation strategies were routinely used and which point of care coagulation tests were in place at the time the studied cases occurred.

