### **Statistical Analysis:**

Summary statistics will be presented as means and standard deviations or medians with interquartile ranges for continuous variables, as appropriate, and frequencies with percentages for categorical variables. All continuous variables will be assessed for normality using the Kolmogorov-Smirnov test. Univariate demographic and covariate comparisons between those who did and did not receive a transfusion will be analyzed using Student’s t-tests or Mann-

Whitney U tests for continuous variables, and Chi-squared or Fisher's Exact tests for categorical variables, as appropriate.

Mixed-effects multivariable linear or logistic regression models will be constructed as necessary. Prior to model entry, all covariates selected for model inclusion will be checked for collinearity using a Pearson correlation matrix. Variable pairs with a correlation  $> 0.70$  will be considered collinear and either combined into one variable, or one of the covariates will be excluded from the model. All variable pairs with a correlation  $\leq 0.70$  will be deemed fit for model entry. Model effect size will be presented as adjusted odds ratios with 95% confidence intervals, or beta coefficients with standard error, as appropriate. The covariates to be included in all models (discussed below) are surgical specialty, age, BMI, sex, presence of coronary artery disease, Elixhauser comorbidities, quarter of the study period, and hemoglobin. Time will be included in all models as a fixed effect by quarter, half-year, or year based on available sample size. The first quarter, half-year, or year will serve as the reference group. The random effects of institution and attending, where appropriate, will be presented as intraclass correlation coefficients and median odds ratios with 95% confidence intervals. Measures of effect size will be reported as adjusted odds ratios for logistic regression and beta coefficients for linear regression, and will be presented with 95% confidence intervals. For logistic regression models, model predictive capability will be presented as the area under the receiver operating curve (ROC) c-statistic. For linear regression, the extent to which the model explains the variability of the data will be presented as  $R^2$  values. Covariates with a statistically significant adjusted odds ratio or beta coefficient (as appropriate) will be considered independent predictors of the outcome.

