## Sample Size:

Based on a rough approximation of the inclusion criteria using DataDirect, we found around 113,000 cases with intraoperative Hemoglobin/Hematocrit values, which should provide sufficient power for all planned analyses.

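### Secondary Outcome 4 enters the Elixhauser comorbidities as a number and again as y/n terms; if the number includes heart failure and cancer, their odds ratios show only the excess over an average comorbidity.

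*Protocol*

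**What the plan says.** In the protocol, Secondary Outcome 4 sets up two mixed-effects logistic models to "determine if surgery type, year, and cardiac disease are independent predictors of intraoperative transfusion". The list of independent variables includes "Elixhauser co-morbidities (as numeric and also CAD y/n, heart failure y/n, cancer y/n". Nothing there says that the three named conditions are taken out of the numeric term. The general covariate list under Methods also puts coronary artery disease (CAD) and the comorbidities side by side without separating them: "presence of coronary artery disease (defined by ICD 9/10 codes), Elixhauser comorbidities, quarter of the study period, and nadir hemoglobin". CAD has its own code list: "we define coronary artery disease based on the present of a discharge ICD9/10 as listed in Appendix 3".

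Two rules under Statistical Analysis bear on how the results will be read:

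- The rule for naming predictors: "Covariates with a statistically significant adjusted odds ratio or beta coefficient (as appropriate) will be considered independent predictors of the outcome".
- The safeguard against overlap: "all covariates selected for model inclusion will be checked for collinearity using a Pearson correlation matrix". Pairs correlated above 0.70 are "either combined into one variable, or one of the covariates will be excluded from the model"; pairs at or below 0.70 are accepted.

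Later in Secondary Outcome 4, a linear model for intraoperative hemoglobin takes over the same covariate list and adds transfusion y/n.

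**The concern.** A condition that is counted in a total and also given its own indicator is in the model twice. The total already gives the patient one unit of comorbidity effect for having the condition. The indicator carries only what is left over. Its OR therefore compares the condition with an average comorbidity, whereas the stated question is whether it predicts transfusion at all.

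This would be harmless if the plan read the two coefficients together. It does not: each covariate is labelled on its own OR. Heart failure is one of two cardiac terms in the list, and Aim 2 and Secondary Outcome 4 both single out cardiac disease. Heart failure or cancer could be reported as not predictive, or even as protective, when the same data show the opposite.

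**Working it through.** **The plan's own figure.** The protocol gives no OR, prevalence or event rate for this model, so there is nothing to reproduce. The only document figure used is the approximate number of cases ("we found around 113,000 cases with intraoperative Hemoglobin/Hematocrit values"), as the size of a simulated data set.

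**Algebra.** Let R be the number of other comorbidities, HF and CA the indicators for heart failure and cancer, and S = R + HF + CA the number that includes them. Suppose

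logit(p) = g·R + h·HF + c·CA + other terms.

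Substituting R = S − HF − CA gives

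logit(p) = g·S + (h − g)·HF + (c − g)·CA + other terms.

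So the reported OR for heart failure is exp(h)/exp(g), the condition's OR divided by the OR per comorbidity. If the number is a weighted score in which the condition has weight w, the divisor is the per-point OR raised to the power w. This only re-expresses the fixed effects, so it does not depend on the random effects.

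**Reported OR for a range of assumed values** (condition's OR ÷ per-comorbidity OR, unweighted count):

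| Condition's OR | per-comorbidity 1.05 | 1.10 | 1.25 | 1.50 |
|---|---|---|---|---|
| 1.10 | 1.05 | 1.00 | 0.88 | 0.73 |
| 1.25 | 1.19 | 1.14 | 1.00 | 0.83 |
| 1.50 | 1.43 | 1.36 | 1.20 | 1.00 |
| 2.00 | 1.90 | 1.82 | 1.60 | 1.33 |

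An intermediate case: 1.16 / 1.105 = 1.05.

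**Simulation check.** One data set of 113,000 cases per scenario, with no random effects. All other inputs are assumptions: 26 other conditions, heart failure base rate 7%, cancer 20%, CAD 15% with OR 1.2 and outside the count, positively correlated comorbidities, and an event rate of about 10% in the two scenarios shown. Each data set was fitted with heart failure and cancer inside the count, then with both removed.

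| Scenario | Term | Inside the count: OR (95% CI), p | Removed from the count: OR (95% CI) |
|---|---|---|---|
| All comorbidity ORs 1.25 | HF | 1.04 (0.98–1.11), p = 0.21 | 1.30 (1.22–1.39) |
| | Cancer | 1.04 (0.99–1.09), p = 0.12 | 1.30 (1.24–1.36) |
| HF 1.10, cancer 1.60, others 1.25 | HF | 0.91 (0.85–0.97), p = 0.006 | 1.14 (1.06–1.21) |
| | Cancer | 1.34 (1.28–1.40), p < 0.001 | 1.67 (1.60–1.74) |

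The fitted count OR was 1.247 in both scenarios, and the identity holds: 1.301/1.247 = 1.043 and 1.135/1.247 = 0.910. Within each scenario the log-likelihood, the count OR and the CAD OR were the same in both fits.

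**The collinearity check.** The simulated correlation of the count with heart failure was 0.25 and with cancer 0.27, far below 0.70, so the pair would pass. If a pair were flagged, the prescribed remedy, combining the two or dropping one, would not take the condition out of the number while keeping its indicator.

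**The case against.** The best defence is that the protocol says only that the comorbidities enter as a number. It does not say whether this is an unweighted count or a weighted score, or which conditions it contains, and such details are often left to an analysis plan. This stands in part: the point has to be conditional, and the divisor depends on the construction. But the protocol itself fixes the covariate form. The bracket presents the three conditions as parts of the Elixhauser term, entered in addition to the number, and a reader following it would count them twice.

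Second, this is a matter of parameterisation, not a biased model. That is correct. Fit and predictions are unchanged, and the full heart failure OR can be recovered (unweighted count) as the count OR times the indicator OR. The plan does not ask for that product, however; it judges each OR alone.

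Third, a reader might infer that the result for CAD, the cardiac factor named in Hypothesis 4, is distorted. The documents do not support that. CAD is defined by its own list in Appendix 3, and nothing settles whether the numeric term also contains it. Where it does not, its OR is untouched, as in the simulation.

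Fourth, a reader might infer that the heart failure and cancer effects will generally vanish or reverse. They need not. For a harmful condition, the OR reaches 1 or falls below it only if the condition's own OR is no larger than the divisor. An OR of 2.00 still reads 1.33 to 1.90 across the range above.

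**Conclusion.** The point holds in conditional form. If the numeric Elixhauser term includes heart failure and cancer, their reported ORs in Secondary Outcome 4 measure excess over the number's per-unit effect. The plan's significance rule can then mislabel a modest effect, while a strong one is only understated. The size cannot be fixed from the documents: every effect size used here is assumed, and the range runs from slight shrinkage (2.00 read as 1.90) to reversal (1.10 read as 0.73).

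The harm is confined to how these indicators are interpreted. The results for surgery type and year, the institution and attending effects, and the observed-versus-expected comparison do not depend on it. In the linear hemoglobin model the same overlap subtracts the per-unit coefficient from each indicator's coefficient.

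**What to change.** In the variable list of Secondary Outcome 4, replace the Elixhauser item with: *number of other Elixhauser comorbidities (excluding any condition entered separately), plus CAD, heart failure and cancer y/n*. If a weighted score is meant, say so and leave out the same conditions. Apply the same wording to the linear hemoglobin model that reuses the list.

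The cost is one phrase in the protocol and one line of code. For an unweighted count or a fixed-weight score, fit and adjustment are identical, so nothing is lost. It also settles the CAD question, because CAD is then outside the number however the index is built.
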